### **7.7.3. Systemic Glucocorticoids**

Chronic systemic glucocorticoid therapy (excluding topical, intraocular, intranasal, intra-articular, or inhaled preparations) is exclusionary if used >14 consecutive days during the 1-month period before study entry (Visit 1) or between study entry (Visit 1) and randomization at Visit 3. Patients who require >14 consecutive days of therapy with these medications after randomization will be excluded from the PP population for analyses.

### **7.7.4. Antihypertensive Medications**

If used, antihypertensive therapy should be kept stable throughout the trial to allow assessments of the effect of randomized therapies on blood pressure (BP). If initiation, discontinuation, or dose adjustment of any BP-lowering agent is medically required at any time during the study, the type and dose of medication must be documented in the eCRF.

## **7.8. Treatment after the End of the Study**

### **7.8.1. Continued Access**

After study treatment is discontinued, an appropriate diabetes treatment regimen will be initiated by the investigator.

## 8. Discontinuation Criteria

### 8.1. Discontinuation from Study Treatment

#### 8.1.1. *Permanent Discontinuation from Study Treatment*

Patients will be permanently discontinued from study drug in the following circumstances:

- if a patient is inadvertently enrolled and it is determined that continued treatment with study drug would not be medically appropriate (see Section 8.1.3)
- if a patient is diagnosed with an active or untreated malignancy (other than basal or squamous cell skin cancer, in situ carcinomas of the cervix, or in situ prostate cancer) after randomization
- if a patient is diagnosed by the investigator with acute or chronic pancreatitis
- if a patient is diagnosed with C-cell hyperplasia or MTC after randomization
- if a patient develops an eGFR  $<30$  mL/min/1.73m^2 as calculated by CKD-EPI
- if the patient or the patient's designee, for example, legal guardian, requests that the patient be withdrawn from study drug
- if the investigator or sponsor decides that the patient should be withdrawn from study drug; if the investigator decides to permanently discontinue study treatment because of an SAE or a clinically significant laboratory value, Lilly or its designee should be alerted immediately
- if the sponsor decides that a treatment arm and patients in that arm should be withdrawn from study drug

Discontinuation of the investigational product for abnormal liver tests **should be considered** by the investigator when a patient meets one of the following conditions after consultation with the Lilly designated medical monitor:

- ALT or aspartate aminotransferase (AST)  $>8 \times$  upper limit of normal (ULN)
- ALT or AST  $>5 \times$  ULN for more than 2 weeks
- ALT or AST  $>3 \times$  ULN and total bilirubin level  $>2 \times$  ULN or prothrombin time  $>1.5 \times$  ULN
- ALT or AST  $>3 \times$  ULN with the appearance of fatigue, nausea, vomiting, right upper-quadrant pain or tenderness, fever, rash, and/or eosinophilia ( $>5\%$ )
- Alkaline phosphatase  $>3 \times$  ULN
- Alkaline phosphatase  $>2.5 \times$  ULN and total bilirubin  $>2 \times$  ULN

- Alkaline phosphatase  $>2.5 \times$  ULN with the appearance of fatigue, nausea, vomiting, right quadrant pain or tenderness, fever, rash, and/or eosinophilia ( $>5\%$ )

Patients who stop the study drug permanently will receive another glucose-lowering intervention (rescue) and will continue participating in the trial according to the protocol to collect all planned efficacy and safety measurements.

### **8.1.2. Temporary Interruption of Study Treatment**

In certain situations after randomization, the investigator may need to temporarily discontinue (interrupt) study drug (for example, due to an AE or a clinically significant laboratory value). If study drug interruption is due to an AE, the event is to be documented and followed according to the procedures in Section 9.2 of this protocol. Investigators should inform the sponsor that study drug has been temporarily interrupted. Every effort should be made by the investigator to maintain patients on study drug and to restart study drug after any temporary interruption, as soon as it is safe to do so. The data related to temporary interruption of study treatment will be documented in source documents and entered in the eCRF.

### **8.1.3. Discontinuation of Inadvertently Enrolled Patients**

If the sponsor or investigator identify a patient who did not meet enrollment criteria and was inadvertently enrolled, a discussion must occur between the sponsor CRP and the investigator to determine if the patient may continue in the study. If both agree it is medically appropriate to continue, the investigator must obtain documented approval from the sponsor CRP to allow the inadvertently enrolled patient to continue in the study with or without treatment with investigational product. Any inadvertently enrolled patient in whom continuous administration of study drug may result in possible or definite safety risk should be discontinued from study drug (see Section 8.1.1).

## **8.2. Discontinuation from the Study**

Every attempt should be made to keep patients in the trial irrespective of their adherence to treatment with study drug in order to minimize the amount of missing data and to enable assessment of study objectives as planned by the study protocol. Patient discontinuation from the study early may be warranted in the following situations for ethical or legal reasons:

- If a patient is diagnosed with T1D
- If a female patient becomes pregnant
- Enrollment in any other clinical trial involving an investigational product or enrollment in any other type of medical research judged not to be scientifically or medically compatible with this study

Patients may also discontinue from the study due to:

- Sponsor or investigator decision when participation in the study needs to be stopped for medical, safety, regulatory, or other reasons consistent with applicable laws, regulations, and good clinical practice (GCP)

- Patient decision when the patient or the patient's designee, for example, legal guardian, requests to be withdrawn from the study

Prior to early study discontinuation, the patient will discontinue study drug and will have end-of-study procedures (ET visit) performed as shown in the Schedule of Activities (Section 2).

During the ET visit, the patient will be prescribed an appropriate glucose-lowering regimen and glucose self-monitoring plan.

### **8.3. Lost to Follow-Up**

A patient will be considered lost to follow-up if he or she repeatedly fails to return for scheduled visits and is unable to be contacted by the study site. Site personnel are expected to make diligent attempts to contact patients who fail to return for a scheduled visit or were otherwise unable to be followed up by the site.

## 9. Study Assessments and Procedures

Section 2 lists the Schedule of Activities, with the study procedures and their timing (including tolerance limits for timing).

[Appendix 2](#) lists the laboratory tests that will be performed for this study.

Unless otherwise stated in the subsections below, all samples collected for specified laboratory tests will be destroyed within 60 days of receipt of confirmed test results. Certain samples may be retained for a longer period, if necessary, to comply with applicable laws, regulations, or laboratory certification standards.

### 9.1. Efficacy Assessments

#### 9.1.1. Primary Efficacy Assessments

The primary efficacy measure is change in HbA1c from baseline at 18 weeks.

#### 9.1.2. Secondary Efficacy Assessments

The following secondary efficacy measures will be evaluated at 18 weeks:

- proportion of patients achieving HbA1c target  $<7.0\%$
- change in body weight from baseline
- change in fasting serum glucose (central laboratory) from baseline

#### 9.1.3. Exploratory Efficacy Assessments

The following exploratory efficacy measures will be evaluated at 18 weeks:

- proportion of patients achieving HbA1c target  $\leq 6.5\%$
- change in 6-point SMPG profile from baseline
- change in fasting plasma glucagon from baseline
- change in HOMA-IR and HOMA-%B from baseline

#### 9.1.4. Appropriateness of Assessments

Efficacy and safety assessments included in this study are generally regarded as reliable and accurate with respect to the efficacy and safety assessments in individuals and populations with T2D.

#### 9.1.5. Body Weight, Height, and Body Mass Index

Body weight will be measured at prespecified time points (see Schedule of Activities, Section 2). Each patient's weight should be measured according to a standardized protocol ([Appendix 7](#)). Body mass index will be computed from the patient's weight and height.

## 9.2. Adverse Events

Investigators are responsible for monitoring the safety of patients who have entered this study and for alerting Lilly or its designee to any event that seems unusual, even if this event may be considered an unanticipated benefit to the patient.

The investigator is responsible for the appropriate medical care of patients during the study.

Investigators must document their review of each laboratory safety report.

The investigator remains responsible for following, through an appropriate health care option, AEs that are serious or otherwise medically important, considered related to the investigational product or the study, or that caused the patient to discontinue the investigational product before completing the study. The patient should be followed until the event resolves, stabilizes with appropriate diagnostic evaluation, or is reasonably explained. The frequency of follow-up evaluations of the AE is left to the discretion of the investigator.

Lack of drug effect is not an AE in clinical studies, because the purpose of the clinical study is to establish treatment effect.

After the informed consent form (ICF) is signed, study site personnel will record via eCRF the occurrence and nature of each patient's preexisting conditions, including clinically significant signs and symptoms of the disease under treatment in the study. In addition, site personnel will record any change in the condition(s) and any new conditions as AEs. Investigators should record their assessment of the potential relatedness of each AE to study procedure, investigational product, and study device via eCRF.

The investigator will interpret and document whether or not an AE has a reasonable possibility of being related to study treatment, study device, or a study procedure, taking into account the disease, concomitant treatment or pathologies.

Planned surgeries and nonsurgical interventions should not be reported as AEs unless the underlying medical condition has worsened during the course of the study.

If a patient's investigational product is discontinued as a result of an AE, study site personnel must report this to Lilly or its designee via eCRF, clarifying if possible, the circumstances leading to any dosage modifications, or discontinuations of treatment.

### 9.2.1. *Serious Adverse Events*

An SAE is any AE from this study that results in 1 of the following outcomes:

- death
- initial or prolonged inpatient hospitalization
- a life-threatening experience (that is, immediate risk of dying)
- persistent or significant disability/incapacity
- congenital anomaly/birth defect

- considered significant by the investigator for any other reason: important medical events that may not result in death, be life-threatening, or require hospitalization may be considered serious, based upon appropriate medical judgment.

Although all AEs occurring after signing the ICF are recorded in the eCRF, SAE reporting begins after the patient has signed the ICF and has received investigational product. However, if an SAE occurs after signing the ICF, but prior to receiving investigational product, it needs to be reported ONLY if it is considered reasonably possibly related to study procedure.

Study site personnel must alert Lilly or its designee of any SAE within 24 hours of investigator awareness of the event via a sponsor-approved method. If alerts are issued via telephone, they are to be immediately followed with official notification on study-specific SAE forms. This 24-hour notification requirement refers to the initial SAE information and all follow-up SAE information.

Pregnancy (during maternal or paternal exposure to investigational product) does not meet the definition of an AE. However, to fulfill regulatory requirements, any pregnancy should be reported following the SAE process to collect data on the outcome for both mother and fetus.

Investigators are not obligated to actively seek AEs or SAEs in subjects once they have discontinued and/or completed the study (the patient summary CRF has been completed). However, if the investigator learns of any SAE, including a death, at any time after a subject has been discharged from the study, and he/she considers the event reasonably possibly related to the study treatment or study participation, the investigator must promptly notify Lilly.

#### **9.2.1.1. Suspected Unexpected Serious Adverse Reactions**

Suspected unexpected serious adverse reactions (SUSARs) are serious events that are not listed in the IB and that the investigator identifies as related to investigational product or procedure. United States 21 CFR 312.32 and European Union Clinical Trial Directive 2001/20/EC and the associated detailed guidance or national regulatory requirements in participating countries require the reporting of SUSARs. Lilly has procedures that will be followed for the recording and expedited reporting of SUSARs that are consistent with global regulations and the associated detailed guidance.

#### **9.2.2. Adverse Events of Special Interest**

##### **9.2.2.1. Hypoglycemia and Hyperglycemia**

Patients will collect information on episodes of hypoglycemia starting from Visit 2 until the last study visit (Visit 801 or ET visit). For that purpose, patients will be trained about signs and symptoms of hypoglycemia, how to treat hypoglycemia, and how to collect in the study diary appropriate information for each episode of hypoglycemia according to the Schedule of Activities (Section 2). Site personnel will enter this information into the eCRF at each visit.

Investigators should use the following definitions and criteria when diagnosing and categorizing an episode considered to be related to hypoglycemia (the PG values in this section refer to values determined by a laboratory or International Federation of Clinical Chemistry and Laboratory Medicine plasma-equivalent glucose meters and strips) (American Diabetes Association 2005):

- **Documented symptomatic hypoglycemia** is defined as any time a patient feels that he/she is experiencing symptoms and/or signs associated with hypoglycemia, and has a PG level of  $\leq 70$  mg/dL ( $\leq 3.9$  mmol/L).
- **Asymptomatic hypoglycemia** is defined as any event not accompanied by typical symptoms of hypoglycemia, but with a measured PG  $\leq 70$  mg/dL ( $\leq 3.9$  mmol/L).
- **Probable symptomatic hypoglycemia** is defined as an event during which symptoms of hypoglycemia are not accompanied by a PG determination (but that was presumably caused by a PG concentration  $\leq 70$  mg/dL [ $\leq 3.9$  mmol/L]).
- **Severe hypoglycemia** is defined as an episode requiring the assistance of another person to actively administer carbohydrate, glucagon, or other resuscitative actions. These episodes may be associated with sufficient neuroglycopenia to induce seizure or coma. Plasma glucose measurements may not be available during such an event, but neurological recovery attributable to the restoration of PG to normal is considered sufficient evidence that the event was induced by a low PG concentration.
- **Nocturnal hypoglycemia** is defined as any hypoglycemic event that occurs between bedtime and waking.

For additional analysis, hypoglycemia defined as glucose  $< 54$  mg/dL ( $< 3.0$  mmol/L) will also be considered.

Cases of relative hypoglycemia are defined as symptomatic events during which the person reports any of the typical symptoms of hypoglycemia and interprets those as indicative of hypoglycemia, but a measured PG concentration  $> 70$  mg/dL ( $> 3.9$  mmol/L) is collected.

If a hypoglycemic event meets the criteria of severe, it needs to be recorded as serious on the AE CRF and reported to Lilly as an SAE.

In each case of suspected or confirmed hypoglycemia, it is important that the event be properly categorized, the effect of the intervention be assessed, and the frequency of hypoglycemia be evaluated. The role of dietary changes and physical exercise (or any other contributing factor) in the development of an event should be established. The patient should receive additional education, if deemed appropriate. Management of increased risk of hypoglycemia is described in Section [7.4.1.2](#).

Severe, persistent hyperglycemia will be collected during the trial to assess the risk of extreme imbalance in glycemic control. Events of interest related to hyperglycemia include rescue therapy for severe, persistent hyperglycemia, per criteria specified in Section [7.4.1.3](#).

### 9.2.2.2. Pancreatitis

Acute pancreatitis is defined as an AE of interest in all trials with dulaglutide, including this trial. Acute pancreatitis is an acute inflammatory process of the pancreas that may also involve peripancreatic tissues and/or remote organ systems (Banks and Freeman 2006). The diagnosis of acute pancreatitis requires 2 of the following 3 features:

- abdominal pain, characteristic of acute pancreatitis (generally located in the epigastrium and radiates to the back in approximately half the cases [Banks and Freeman 2006; Koizumi et al. 2006]; the pain is often associated with nausea and vomiting);
- serum amylase (total and/or pancreatic) and/or lipase  $\geq 3 \times$  ULN
- characteristic findings of acute pancreatitis on computed tomography (CT) scan or magnetic resonance imaging (MRI).

If acute pancreatitis is suspected, appropriate laboratory tests (including levels of pancreatic amylase and lipase) should be obtained via the central laboratory (and locally, if needed). Imaging studies, such as abdominal CT scan with or without contrast, MRI, or gallbladder ultrasound, should be performed. If laboratory values and/or abdominal imaging support the diagnosis of acute pancreatitis, the patient must discontinue therapy with investigational product, but will continue in the study on another glucose-lowering regimen (see Sections 7.7.1 and 8.1.1 for details on rescue intervention). The most appropriate diabetes therapeutic regimen will be decided by the investigator, based on the patient's clinical status. A review of the patient's concomitant medications should be conducted to assess any potential causal relationship with pancreatitis.

Each case of AE of pancreatitis must be reported. If typical signs and/or symptoms of pancreatitis are present and confirmed by laboratory values (lipase or amylase [total and/or pancreatic]) and imaging studies, the event must be reported as an SAE. For a potential case that does not meet all of these criteria, it is up to the investigator to determine the seriousness of the case (AE or SAE) and the relatedness of the event to study drug.

In addition to the diagnostic assessment in patients who develop symptoms of acute pancreatitis, each patient will have measurements of pancreatic amylase and lipase at screening, baseline, Visit 6 (Week 6), Visit 12 (Week 18), and the last study visit (Visit 801 [Week 22] or ET visit), to assess any potential effects of dulaglutide on the exocrine pancreas (refer to the Schedule of Activities, Section 2). Further diagnostic assessment per Lilly algorithm for assessment of asymptomatic pancreatic hyperenzymemia will be required whenever lipase and/or pancreatic amylase are  $\geq 3 \times$  ULN at any time during the study. If this situation occurs at Visit 801 (Week 22), the patient will be required to undergo this additional work-up, and the data will be collected in the clinical trial database.

All suspected cases of acute or chronic pancreatitis, as well as cases of confirmed lipase or pancreatic amylase values  $\geq 3 \times$  ULN, will be adjudicated by an independent committee of expert physicians. In addition, AEs of severe or serious abdominal pain of unknown etiology will also be submitted to the adjudication committee to assess for possible pancreatitis or other pancreatic

disease. Relevant data from patients with acute or chronic pancreatitis, those with severe or serious abdominal pain, and those that undergo additional assessments due to confirmed hyperenzymemia will be entered into a specifically designed eCRF page by study site or Lilly staff. The adjudication committee representative will enter the results of adjudication in a corresponding eCRF page.

#### **9.2.2.3. C-Cell Hyperplasia and C-Cell Neoplasms**

Individuals with personal or family history of certain thyroid or nonthyroid endocrine abnormalities or certain preexisting laboratory and genetic characteristics will be excluded from the study (see Section 6.2). The assessment of thyroid safety during the trial will include reporting of thyroid treatment-emergent AEs (TEAEs) and measurements of calcitonin according to the Schedule of Activities (Section 2) at screening, baseline, and Visit 12 (Week 18) or ET visit. The purpose of calcitonin measurements is to assess the potential of dulaglutide to affect thyroid C-cell function, which may indicate development of C-cell hyperplasia and neoplasms.

Patients who develop serum calcitonin increases  $\geq 50\%$  of the mean of the baseline and screening values AND an absolute value  $\geq 20$  pg/mL and  $< 35$  pg/mL at Visit 12 (Week 18) will be asked to repeat the measurement within 1 month. If this repeat value is increasing ( $\geq 10\%$  increase), the patient will be encouraged to undergo additional endocrine assessment and longer-term follow-up by an endocrinologist to exclude a serious adverse effect on the gland.

Patients with an increase in serum calcitonin  $\geq 50\%$  of the mean of the baseline and screening values AND an absolute value  $\geq 35$  pg/mL at Visit 12 (Week 18) will be recommended to immediately undergo additional endocrine assessments and longer-term follow-up by an endocrinologist.

For patients who require additional endocrine assessment because of increased calcitonin concentration per criteria provided in this section, data from the follow-up assessment will be collected in the specific section of the eCRF.

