HbA1c	X		X			X				X		X	X	X	
Glucose (fasting) m			X			X				X		X	X	X	
Pancreatic amylase, lipase	X		X			X						X	X	X	
Serum insulin (fasting) m			X									X		X	
C-peptide			X									X		X	
Plasma glucagon (fasting) m,p			X			X						X		X	
Calcitonin	X		X									X		X	
Pharmacogenetic			X												
Nonpharmacogenetic biomarker (plasma and serum)			X		X	X						X		X	
PK samples															
PK samples			X q	X r	X q	X s					X t		X u	X u	X u

Abbreviations: BP = blood pressure; CKD-EPI = Chronic Kidney Disease-Epidemiology; ECG = electrocardiogram; eGFR = estimated glomerular filtration rate; ET = early termination; HbA1c = hemoglobin A1c; OAM = oral antihyperglycemia medication; PG = plasma glucose; PK = pharmacokinetic; PR = pulse rate; SMPG = self-monitored plasma glucose.

- a Patients who are unable or unwilling to continue in the study because of an adverse event or any other reason will perform an ET visit as their final study visit. If the patient is discontinuing during an unscheduled visit, that visit should be performed as the ET visit. If the patient is discontinuing during a scheduled visit, that visit should be considered the ET visit.
- b The visit date is determined in relation to the date of the randomization visit ( $\pm$  the allowed visit window).
- c Baseline assessments must be completed before processing in the interactive web-response system (IWRS).
- d ECGs will be performed in triplicate. ECGs occurring on visits with PK collection should be measured at least 30 minutes prior to obtaining the sample for PK measurement.
- e 6-point SMPG consists of measurements before and 2 hours after each of 3 main meals within the same day. These SMPG profiles are collected by the patient within 1 week prior to the assigned visits.
- f If performed prior to visit.
- g All training should be repeated as needed to ensure patient compliance.
- h Patients should administer their first dose of study drug at the end of this visit, after other study procedures and randomization. Patients will be encouraged to administer their weekly dose of study drug in the clinic, when possible, at subsequent visits.
- i Study drug compliance will be reviewed for the time period from Visit 4 to Visit 12 and entered in the eCRFs at Visit 6, Visit 10, Visit 11, and Visit 12 for the interval after the previous compliance entry.

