#### **9.4.2. Laboratory Tests**

For each patient, laboratory tests detailed in [Appendix 2](#) should be conducted according to the Schedule of Activities (Section 2).

Any clinically significant findings from laboratory tests that result in a diagnosis and that occur after the patient receives the first dose of investigational product should be reported to Lilly or its designee as an AE via eCRF.

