#### **9.4.3. Safety Monitoring**

Lilly will periodically review evolving aggregate safety data within the study by appropriate methods, including trends in safety variables, laboratory analytes, and AEs. An AC will review prespecified safety reports in an unblinded fashion. In addition, the study team will review safety reports in a blinded fashion according to the schedule provided in the Trial-Level Safety Review plan. Lilly will also review SAEs within time frames mandated by company procedures. The Lilly CRP will, as appropriate, consult with the functionally independent Global Patient Safety therapeutic area physician or clinical scientist.

In addition, specific safety measures are included in the protocol to ensure appropriate monitoring of pancreatic, thyroid, and liver safety. Laboratory findings that trigger pancreatic and thyroid safety monitoring per Lilly standards are provided in Sections [9.2.2.2](#) and [9.2.2.3](#), respectively. Details of liver safety monitoring are provided in [Appendix 4](#). If a study patient experiences elevated ALT  $\geq 3 \times$  ULN, alkaline phosphatase  $\geq 2 \times$  ULN, or elevated total bilirubin  $\geq 2 \times$  ULN, clinical and laboratory monitoring should be initiated by the investigator per Lilly Hepatic Safety Monitoring Algorithm. Details for hepatic monitoring depend upon the severity and persistence of observed laboratory test abnormalities. To ensure patient safety and comply with regulatory guidance, the investigator is to consult with the Lilly CRP regarding collection of specific recommended clinical information and follow-up laboratory tests. See [Appendix 4](#).

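### Both calcitonin action rules name only Visit 12, so a qualifying early-termination value triggers no calcitonin-specific repeat, referral or required follow-up eCRF entry

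*Protocol*

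**What the plan says.** Protocol 9.2.2.3 (C-Cell Hyperplasia and C-Cell Neoplasms) sets the sampling times: calcitonin is measured "at screening, baseline, and Visit 12 (Week 18) or ET visit". The Schedule of Activities agrees. Its calcitonin row is marked at Visits 1, 3, 12 and ET, and not at Visit 801.

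Two action rules follow. Each needs a rise of at least 50% over the mean of the screening and baseline values.

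- **20 to <35 pg/mL:** such patients "at Visit 12 (Week 18) will be asked to repeat the measurement within 1 month". If the repeat is at least 10% higher, endocrine assessment is encouraged.
- **35 pg/mL or more:** such patients "at Visit 12 (Week 18) will be recommended to immediately undergo additional endocrine assessments and longer-term follow-up by an endocrinologist".

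A closing sentence covers data capture. For patients who need endocrine assessment "per criteria provided in this section, data from the follow-up assessment will be collected in the specific section of the eCRF".

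Under footnote a of the Schedule of Activities, patients who leave the study "will perform an ET visit as their final study visit". Protocol 9.4.3 adds no thyroid trigger of its own and sends the reader back: "Laboratory findings that trigger pancreatic and thyroid safety monitoring per Lilly standards are provided in Sections" 9.2.2.2 and 9.2.2.3.

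**The concern.** The measurement sentence names the ET visit and the action sentences do not. The eCRF sentence relies on the section's own criteria, so it carries the same limit. A completer with 40 pg/mL and a 50% rise at Visit 12 is advised to see an endocrinologist at once, and the findings are recorded. An early leaver with the same value at ET meets neither rule as written.

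At stake is consistent safety follow-up for an adverse event of special interest, in a trial of two doses above the approved range. Early leavers also lack the Visit 801 contact that completers have about four weeks after Visit 12, so the written prompt does more for them.

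**Working it through.** The plan states no figure for this point. The check is a comparison of texts, followed by two small calculations.

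**Step 1: what applies at each visit**

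| Item | Visit 12 | ET visit |
|---|---|---|
| Calcitonin drawn (9.2.2.3; Schedule of Activities) | yes | yes |
| Repeat rule, 20 to <35 pg/mL (9.2.2.3) | yes | not named |
| Referral rule, 35 pg/mL or more (9.2.2.3) | yes | not named |
| Required follow-up eCRF entry (9.2.2.3) | yes, through the rules | not reached |
| Listing of a qualifying rise (SAP 6.13.4.4) | yes | yes, any value after first dose |
| Later scheduled study visit | Visit 801 | none |

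The SAP would therefore list an ET rise for which the protocol writes no calcitonin-specific step.

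**Step 2: does another section fill the gap?** Protocol 9.4.3 points back to 9.2.2.3. Protocol 9.2 gives a general duty: "Investigators must document their review of each laboratory safety report". Protocol 9.4.2 requires adverse event reporting for "Any clinically significant findings from laboratory tests that result in a diagnosis". None of these directs a calcitonin repeat or a referral. By contrast, the pancreatic enzyme work-up in 9.2.2.2 applies at any point in the study, Visit 801 included.

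**Step 3: who could come under the rules.** Inputs from Protocol 10.1: about 300 randomized 1:1:1:1, 20% dropout.

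- The plan's own completer figure first: 75 × (1 − 0.20) = 60 per arm, or 240 in all, as stated.
- Early leavers: 0.20 × 300 = 60.
- On dulaglutide, if dropout is even across arms: 60 × 3/4 = 45.
- If dropout were 10% to 30% (assumed range): 30 to 90 patients.

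These are upper bounds. Patients lost to follow-up (8.3) may have no ET sample. Patients who only stop study drug stay in the trial (5.1, 8.1.1), reach Visit 12 and are not affected.

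**Step 4: which ET values would qualify.** A rise of at least 50% means that the value is at least 1.5 times the pre-dose mean.

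- At 20 pg/mL, the pre-dose mean must be at most 20/1.5 = 13.3 pg/mL.
- At 35 pg/mL, it must be at most 35/1.5 = 23.3 pg/mL.
- Exclusion criterion 25 removes patients at 20 pg/mL or more at study entry. If the Visit 3 value is also below 20 (assumption), the pre-dose mean is below 20. Since 35/20 = 1.75, any value of 35 or more is then a rise of more than 75% and always meets the second rule's conditions.

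The documents give no rate of qualifying rises, so the number of patients affected cannot be calculated.

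**The case against.** The strongest reply is that the general safety provisions already catch such a value. The adverse event definition in Protocol Appendix 1 includes an abnormal laboratory finding, so a raised ET calcitonin can be an adverse event without a diagnosis. Protocol 9.2 then has the investigator follow medically important events until they resolve, stabilize after work-up or are explained. The sponsor also reviews laboratory trends (9.4.3). This stands. A reader might infer that the plan provides no written action at all for an ET value, and the documents do not support that. What is missing is the calcitonin-specific prompt with its thresholds. The general route depends on the investigator judging the event medically important.

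A second reply is that Visit 12 is shorthand for the end-of-treatment draw. The sampling sentence pairs the two visits, and the calcitonin row of SAP Appendix 1 places values from day 2 to the end of maintenance in the Visit 12 window. This makes an oversight the likely explanation. A reader might infer that the sponsor chose to exclude ET values, and nothing in the documents suggests so. But the window is an analysis rule and directs no care. The same table also lists serum calcitonin in the amylase and lipase row with different windows, so it is weak evidence of intent.

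A third reply is that the practical loss is small. The Visit 12 actions are requests and recommendations, and completers have no later scheduled calcitonin draw either. Both points are right. An early leaver loses a written prompt and a required data entry, not a mandatory test.

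**Conclusion.** The inconsistency is real on the text. A qualifying calcitonin at ET triggers no calcitonin-specific repeat, referral or required follow-up eCRF entry, while the same value at Visit 12 does. It is best described as a drafting inconsistency.

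The bound of about 60 early leavers (about 45 on dulaglutide) rests on the planned 20% dropout, and the dulaglutide share also on even dropout. It counts people who could come under the rules and should not be read as a count of people with a raised value. That count is probably very small. Calcitonin does not enter the primary analysis, so sample size, power and the primary comparison are untouched.

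A reader might also infer that the follow-up eCRF section closes at ET. The documents do not say so, and nothing bars an entry for an ET case. The wording only fails to require one.

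The change is still worth making, because it improves follow-up on an event of special interest at almost no cost.

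**What to change.** In both action rules of Protocol 9.2.2.3, add *or the ET visit* directly after the reference to Visit 12 (Week 18). The eCRF sentence refers to the section's own criteria, so it will then cover ET cases without a separate change. The SAP listing already includes these values and needs no edit for this point.

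The cost is a few words in two sentences, plus a repeat sample or referral offered to probably very few patients. The downside is that some early leavers will decline or be unreachable, so their follow-up may stay incomplete.
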